6.5 Analysis populations

The primary trial efficacy analysis will be done in the intention-to-treat (ITT) population, including all randomly assigned participants.

A secondary analysis will be performed in the persistent population (PP, i.e. including all patients who persisted on the investigational drugs for at least 4 and 8 months (ACiGaN trial) or 10 months (CHRONiGaN trial).

Patients who need to change their study treatment prior to 1st month (ACiGaN trial) or 4 months (CHRONiGaN trial) will be considered as dropouts.

The safety population will be represented by all patients receiving at least one dose of the investigational drugs.

A recent systematic review (15) evidenced that patients with histological lesion M1 were responsive to corticosteroids. Therefore, we will do a subgroup analysis to evaluate the effect of corticosteroids in active and chronic IgAN patients with lesion M1 versus M0.

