
Study Products
	
Methylprednisolone succinate and prednisone (Corticosteroids, CS) Dapagliflozin (Sodium-glucose cotransporter 2 inhibitor, SGLT2i)

Treatments
	
ACiGaN Study
 
IgAN Active renal lesions
 
Experimental arm: Corticosteroids + RASBs (4 months) → RASBs (4 months) → RASBs (28 months)
 
Control arm (KDIGO): RASBs (4 months) → RASBs + Corticosteroids (4 months) → RASBs (28 months)
 <hr/> 
CHRONiGaN Study
 
IgAN Chronic renal lesions Moderate renal lesions
 
Experimental arm: RASBs (4 months) → RASBs + Dapagliflozin (6 months) → RASBs + Dapa (26 months)
 
Control arm (KDIGO): Run-in → RASBs + Corticosteroids (6 months) → RASBs (26 months)
 
Patients will be randomized separately in each trial (allocation 1 to 1 ratio). Stratified randomization will be done by age and sex in renal centers.
 
ACiGaN trial
 
Experimental arm: Early corticosteroids therapy combined with RASBs followed by RASBs treatment.
 
Control arm (standard care): RASBs treatment followed by corticosteroids combined with RASBs and then only RASBs.
 
CHRONiGaN trial
 
Experimental arm: RASBs therapy followed by Dapagliflozin combined with RASBs.
 
Control arm (standard care): RASBs therapy followed by Corticosteroids combined with RASBs and then RASBs alone

Sample Size and Statistics
	
ACiGaN. Data from the literature have shown a difference in renal survival between corticosteroids and controls when the researchers assumed a difference of 50% in the primary end point (i.e., in the between-arms difference of delta 24 hour proteinuria from base-line to 6 months) as clinically relevant. Therefore, we assume that a mean delta proteinuria from base-line to 6 months in patients treated with RASBs alone (control arm) is 0.6 ± 1.0 g/24 hours (\pmSD) versus a mean delta proteinuria 1.2 ± 1.0 g/24 hours (\pmSD) from base-line to 6 months in patients treated with RASBs and corticosteroids (experimental arm). Based on these assumptions, we calculated a sample size of 132 patients (66 patients per group including a 10% dropout rate) for a power of 90%, a two-sided significance level of 0.05 and 3 years

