4.3 Interventions

4.3.1 Study treatments (dosage and rationale)

Study drugs (already been placed on the market as authorized medicinal products) will be not supplied by the study Sponsor and will be administered according their labelling and no additional labelling will be required to ensure subject safety and the reliability and robustness of data generated in this clinical trial.

For all information about study drugs, please refer to their respective Summary of Product Characteristics (SmPCs).

RASBs

Patients will receive treatment with renin-angiotensin system blockers, RASBs (either angiotensin-converting enzyme inhibitor, ACEi, or angiotensin II receptor blocker, ARB) as per clinical practice, according to the current KDIGO guidelines.

For example, Ramipril will be administered at dosage of 5 mg x 2 times per day (8.00-20.00) in patients with blood hypertension. Then, it will be increased of 2.5 mg x 2 per day every three days until the reduction of hypertension and proteinuria.

In patients with normal arterial blood pressure Ramipril will be administered at dosage of 2.5 mg x 2 times a day

In patients no tolerant to Ramipril, a sartan will be administered, i.e. Losartan 12.5 mg x 2 times a day. A gradual increase of 6.25 mg (two times a day) will be done to reduce proteinuria.

Rationale: RASBs will be administered to reduce blood pressure at glomerular level and proteinuria (39,40).

Dapagliflozin

The drug will be administered at dosage of 10 mg per day as reported in other randomized clinical trials in which Dapagliflozin has been administered in combination with RASBs (29,31).

Rationale: To reduce blood pressure at glomerular level and proteinuria.

Corticosteroids

AClIgAN trial

Methylprednisolone will be administered at dosage of 15 mg/kg body weight until the dosage of 1 gr in the first day and 50% reduced dose in the other two days and then Prednisolone at dosage of 0.5 mg/kg body weight at alternate days will be administered until the end of the month. This treatment will be repeated for 3 consecutive months. After 3 months, prednisone will be gradually reduced of 25% of the dosage every week until the end of treatment (4 weeks).

Rationale: To care the active renal lesions represented by endocapillary and extracapillary glomerular lesions. This treatment has been used in other clinical trials of IgAN (12,18,43).

CHRONlIgAN trial

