4.7 End of Study and Patient withdraw

The end of the study is defined as the last visit of the last enrolled subject.

A visit of end of study will be performed 30 days after last treatment to collect data about any adverse events and other administered therapies.

The withdraw of enrolled patients from study treatment and/or from the whole study will be done in the following conditions:

- withdraw of the informed consent
- pregnancy
- superimposed malignant diseases
- kidney failure (end-stage kidney disease)
- dialysis
- renal transplant
- non-compliance with study procedures
- Investigator judgment, for any ethical, medical, or scientific reasons
- Death.

The patient may withdraw from the treatment/trial, at any time, without penalty or loss of benefits to which he/she is otherwise entitled.

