7.4 Harms

Safety information will be collected for the intention-to-treat population by recording severe adverse events (SAEs). Upon confirmation, the severity of the AEs will be evaluated for the procedures conducted, the outcomes and the relationships to the study drugs. The AEs will be reported to the principal investigator who will confer with an independent monitoring committee whose members will not know the trial-group assignment. The monitoring committee will evaluate the trial safety and, independently, will determine any necessary revisions to the trial design and will validate all decisions for continuing the trial.

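### The persistent (PP) and safety sets in Section 6.5 rest on an undefined term, investigational drugs, and do not work on the protocol's own list of study products

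*Protocol*

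**What the plan says.** Section 6.5 of the protocol sets the primary efficacy analysis in all randomised patients. It then adds three rules:

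- A secondary PP (persistent) population, "including all patients who persisted on the investigational drugs for at least 4 and 8 months (ACiGaN trial) or 10 months (CHRONiGaN trial".
- A dropout rule: "Patients who need to change their study treatment prior to 1st month (ACiGaN trial) or 4 months (CHRONiGaN trial) will be considered as dropouts".
- A safety rule: "The safety population will be represented by all patients receiving at least one dose of the investigational drugs".

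The term investigational drugs is not defined. Under Study Products the Synopsis names "Methylprednisolone succinate and prednisone (Corticosteroids, CS) Dapagliflozin (Sodium-glucose cotransporter 2 inhibitor, SGLT2i" and nothing else. Section 1.3 (Study products) covers the same drugs, and RASBs stand apart in Section 1.4. Section 4.3.1, however, describes RASBs under study treatments: "Patients will receive treatment with renin-angiotensin system blockers, RASBs".

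Section 7.4 names a different population for harms: "Safety information will be collected for the intention-to-treat population by recording severe adverse events (SAEs". Section 4.7 includes "non-compliance with study procedures" among the reasons for withdrawing a patient from treatment, from the whole study, or both. Section 6.4 states that the ITT analysis keeps all randomised patients whether or not they adhere.

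**The concern.** In ACiGaN the two arms receive the same steroid course at different times. In CHRONiGaN they receive different drugs for very different durations. A population rule based on time on drug therefore cannot be neutral between arms unless it refers to what each arm was assigned.

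Three things are at stake:

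- **PP analysis.** If the set is empty or one-armed on a plausible reading, the secondary analysis either cannot be run or will be redefined after open-label data have been seen.
- **ACiGaN safety comparison.** The trial asks whether giving steroids early is worth the harm. If entry to the control safety set depends on still having proteinuria at month 4, membership depends on a post-randomisation response in one arm only. The controls left out are the ones never exposed to steroids.
- **ITT completeness.** ITT requires outcomes as well as membership. Patients who leave the study for non-compliance remain in the ITT set by name but have no later proteinuria or eGFR values.

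**Working it through.** **1. The plan's own figure.** With a difference of 0.6 g/24 h, SD 1.0, two-sided 0.05 and 90% power (Section 6): n per arm = 2 × (1.960 + 1.282)² × 1.0² / 0.6² = 58.4, so 59. Allowing for 10% dropout, 59 / 0.9 = 65.6, so 66 per arm and 132 in total. This matches the protocol. Nothing below changes it: 66 × 0.9 = 59.4 evaluable per arm gives 90.5% power.

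**2. Months on a listed study product by study month m.** Regimens are from Sections 3 and 4.3.1. CS = corticosteroids.

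- ACiGaN experimental, CS in months 0-4: min(m, 4)
- ACiGaN control, CS in months 4-8: max(0, min(m − 4, 4))
- CHRONiGaN experimental, dapagliflozin for 32 months after a 4-month run-in: max(0, min(m − 4, 32))
- CHRONiGaN control, CS for 6 months after the same run-in: max(0, min(m − 4, 6))

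| Trial | Study month | Experimental | Control |
|---|---|---|---|
| ACiGaN | 4 | 4 | 0 |
| ACiGaN | 8 | 4 | 4 |
| ACiGaN | 36 | 4 | 4 |
| CHRONiGaN | 10 | 6 | 6 |
| CHRONiGaN | 14 | 10 | 6 |
| CHRONiGaN | 36 | 32 | 6 |

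**3. PP rule against the table.** In ACiGaN, 8 months is unreachable in either arm. The 4-month criterion, applied at month 4, keeps experimental patients only. In CHRONiGaN, 10 months on drug is first reached at month 14 in the experimental arm and never in the control arm.

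**4. PP rule on the other readings.**

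- *RASBs counted as investigational.* Both arms can qualify. But RASBs are given in both arms, and the inclusion criteria admit patients already taking them. Someone who stopped steroids after the first pulse but stayed on RASBs for 8 months would count as persistent.
- *Persistence on the assigned sequence up to month 4, 8 or 10.* Both arms can qualify and the set is meaningful. Section 6.5 does not say this.

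**5. Safety set.** On the product list, an ACiGaN experimental patient enters at the first pulse. A control enters only on starting steroids after month 4. Section 1.2 makes that start conditional on persistent proteinuria and adequate eGFR, whereas the treatment sequences in the Synopsis, Section 3 and Figure 2A show it without the condition. The protocol gives no rate for controls who never start, so let r be that proportion (an assumption):

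Controls in the safety set = 66 × (1 − r)

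| r | Controls in set | Controls lost |
|---|---|---|
| 0 | 66 | 0 |
| 0.10 | 59.4 | 6.6 |
| 0.30 | 46.2 | 19.8 |
| 0.50 | 33 | 33 |

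In CHRONiGaN both listed drugs start at month 4, so patients who leave during run-in are lost from both arms and no imbalance is built in.

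**6. Safety wording.** Section 6.5 uses patients dosed with investigational drugs. Section 7.4 uses the ITT population and mentions only SAEs. Section 5.3 records all AEs and SAEs from consent to 30 days after last treatment. Section 5.1.1 classes events before the first investigational product as non-treatment-emergent. On the narrow reading, that covers months 0-4 in ACiGaN controls, which is the comparison period for early steroids.

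**7. Dropouts and withdrawal.** Section 6.5 attaches no consequence to the dropout label. Section 4.7 permits, but does not require, withdrawal from the whole study for non-compliance.

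**The case against.** The strongest reply is that the sets are not really empty. Section 4.3.1 treats RASBs as a study treatment, Section 1.5 lists their risks alongside the other study drugs, and Figures 2A and 2B draw each arm's intervention as one sequence including RASBs. Section 6.5 itself dates a CHRONiGaN change of study treatment to before month 4, when only RASBs are given. The 4, 8 and 10 months also match the endpoint times in Section 4.4. The intended meaning may well be persistence on the assigned sequence. This stands as far as it goes: a reader might infer that the PP analysis definitely cannot be computed, and the protocol does not support so firm a statement. It supports an undefined term that fails on one documented reading, loses its purpose on a second, and works only on a third that is not written down.

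A reader might also infer that early switchers and non-compliers are excluded from ITT and bias the primary result. The text does not say so. Sections 6.4 and 6.5 both fix ITT as all randomised patients, the dropout sentence removes nobody from that set, and Section 4.7 already allows withdrawal from treatment alone. Any figure for ITT bias would rest on an exclusion that the protocol does not state.

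On safety, AEs are recorded from consent for every patient, so the data will exist. The problem is the denominator and the counting window, not collection. Section 7.4 speaks of collection and Section 6.5 of an analysis set, so the two need aligning but are not flatly opposed.

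Finally, detail on analysis sets often sits in a SAP, which is not at hand. Here, though, the protocol has already fixed the rules, and the point concerns what those rules say.

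**Conclusion.** The point holds in limited form and should be fixed. On the protocol's own product list, the 8-month criterion is met by no ACiGaN patient, the 4-month criterion at month 4 by no ACiGaN control, and the 10-month criterion by no CHRONiGaN control. On the same reading, the ACiGaN safety set loses controls from one arm only: about 7-20 of 66 if 10-30% never start steroids, and 0-33 over the range 0-50%. These rates are assumptions. The safety set is not empty, and CHRONiGaN has no built-in safety imbalance.

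The effect is confined to the secondary PP analysis, the ACiGaN safety comparison and the completeness of ITT outcomes. The ITT definition is sound as written and the ACiGaN sample size of 132 is unaffected.

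**What to change.** 1. **PP set.** In Section 6.5, define it as adherence to the assigned treatment sequence, RASBs included, up to the primary assessment time. First reconcile those times: Section 4.4 gives 4 and 8 months (ACiGaN) and 10 months (CHRONiGaN), Section 6 gives 6 months for ACiGaN, and Section 6.4 gives 6 and 12 months respectively.
2. **Safety set.** Define it as all randomised patients who start their assigned strategy, RASBs included, analysed by arm from randomisation with all AEs and SAEs. Align Section 7.4 with this and with Section 5.3.
3. **Dropouts.** State that patients given this label stay in the ITT set and continue to be followed.
4. **Withdrawal.** In Section 4.7, separate stopping study treatment from leaving the study, so that scheduled proteinuria, eGFR and safety assessments continue unless consent is withdrawn.
5. **Control-arm steroids.** Reconcile Section 1.2, where they are conditional, with the sequences shown unconditionally in the Synopsis, Section 3 and Figure 2A. Which is intended is for the sponsor to settle.

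The cost is wording, plus the already scheduled visits for patients who stop or change treatment. The sample size does not change.

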7. DATA MANAGEMENT

7.1 Data collection

Data collection will be done by the participant renal units. To reduce the withdrawn or lost to the follow-up quarterly meetings will be done by webinars.

The designated investigator staff will enter the data required by the protocol into the electronic Case Report Forms (eCRF). Investigator site staff will not be given access to the eCRF until they have been trained.

The Principal Investigator is responsible for assuring that the data entered into eCRF is complete, accurate, and that entry and updates are performed in a timely manner.

7.2 Data management

The processes of acquiring and recording data will be done by the eResult Company through the OMNIACARE platform and the ReCaS data center.

The OMNIACARE will be responsible for the acquisition of data from laboratory and measurement devices and will transfer data to ReCaS data center for their processing. The structure is cloud-based and adopts the HAAS model so that it does not depend on a specific cloud service provider and allows an effective scalability of resources. The activity will consist in transporting data from the devices where they are generated to the computing platform. Solutions will be studied and implemented to enable transparent, efficient and reliable transfer of data from their devices at the laboratory participants in the study to the ReCaS data center where the computing platform are located. Remote access to data will be done by means cloud technologies and secure protocols such as WebDAV and

HTTPS. In addition, Dropbox-like personal storage solution will be deployed, in order to allow, store and manage data, sharing them with partners in a simple way.

7.3 Data monitoring

An Independent Data Monitoring Committee will carry out interim analyses every 12 months. Data will be presented to the Trial Steering Committee. The interim analysis will be performed on the primary end point when 50% of patients will be randomized and completed 6 months of follow-up. The interim analysis will be done by the Coresearch Agency that is an independent statistician company, blinded for the treatment allocation.

In presence of therapy benefit or futility in the experimental arm, the Independent Data Safety Monitoring Board Committee will report to the Central Ethics Committee the interruption of the study.

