6. SAMPLE SIZE AND STATISTICAL METHODS

ACIGAN. Data from the literature (22,23) have shown a difference in renal survival between corticosteroids and controls when the researchers assumed a difference of 50% in the primary end point (i.e. in the between-arms difference of delta 24 hour proteinuria from baseline to 6 months) as clinically relevant. Therefore, we assume that a mean delta proteinuria from baseline to 6 months in patients treated with RASBs alone (control arm) is 0.6 ± 1.0 g/24 hours (\pm SD) versus a mean delta proteinuria that is 1.2 ± 1.0 g/24 hours (\pm SD) from baseline to 6 months in patients treated with RASBs and corticosteroids (experimental arm). Based on these assumptions, we calculated a sample size of

132 patients (66 patients per group including a 10% dropout rate) for a power of 90%, a two-sided significance level of 0.05 and 3 years of recruitment. If the number of the enrolled patients will be insufficient, the recruitment period will be extended for two years.

CHRONiGaN. Data from the literature (29-31) have shown a difference of renal survival between SGLT2is and controls. There are no data in the literature exploring the difference of renal survival or proteinuria between SGLT2is and steroids. Here, the researchers assumed an opportunistic sample of 300 patients for this first comparative study (150 patients per group, including a 10% dropout rate).

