6.4 Statistical Methods

Quantitative variables will be summarized in the presence of normal distribution values as mean \pm SD or median, and interquartile ranges in the presence of non-normally distributed variables. The between-arms comparisons of continuous variables will be performed by independent t-test or Mann-Whitney U test, as appropriate. The between-arms difference of the primary end point (i.e. in the between-arms difference of delta 24h proteinuria from baseline to 6 months in the ACiGAN trial and the between-arms difference of delta 24h proteinuria from baseline to 12 months in the CHRONiGAN trial will be expressed as mean difference and 95% CI. Categorical variables will be presented as absolute and percentage frequency. Proportions will be compared using the Pearson's X^2 test or Fisher's test, as appropriate. The time to event analysis will be performed by the Kaplan-Meier curves by comparing the experimental and control group by the log rank test. Multivariate analysis will be based on Cox's regression proportional hazard method and used to assess the relative risk associated with possible baseline prognostic factors such as sex, age, serum creatinine, eGFR, hypertension, histological lesions and therapy.

The primary analysis will be conducted according to the intention-to-treat approach in all randomized patients, irrespective of adherence to the assigned treatment. A per protocol analysis will be also performed. A secondary analysis by linear mixed models (LMM) or generalized estimating equations (GEE) of repeated measurements of eGFR and proteinuria will be also performed. The choice between the two analyses will closely depend on the distribution type of the outcome variables in our study cohorts.

In these models, data will be expressed as regression coefficients, 95% CIs and P value. All analyses will be performed using SPSS for Windows, 17.0 (SPSS Inc., North Sydney, Australia) and STATA/IC 13.1 for Windows (College Station, Texas, US). A *P* value less than 0.05 will be considered statistically significant.

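### The interim look can stop the trials for benefit with no significance level but 0.05 in the protocol, and its 6-month trigger does not secure CHRONiGaN's primary endpoint

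*Protocol*

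**What the plan says.** Section 7.3 describes the monitoring in two sentences that are not connected to each other. One reads "An Independent Data Monitoring Committee will carry out interim analyses every 12 months. Data will be presented to the Trial Steering Committee". The other reads "The interim analysis will be performed on the primary end point when 50% of patients will be randomized and completed 6 months of follow-up". The action that may follow is set out for the case "In presence of therapy benefit or futility in the experimental arm": the committee reports the interruption of the study to the ethics committee. The section adds that the company doing the interim analysis is blinded to allocation. It gives no stopping limit.

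Section 6.4 closes with a general rule that a P "value less than 0.05 will be considered statistically significant". It makes no exception for interim analyses. Section 6 sizes ACiGaN on a two-sided 0.05. CHRONiGaN has an opportunistic sample of 300 with no stated alpha or power.

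The primary time points differ by section:

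- **Synopsis endpoints and section 4.4:** 4 and 8 months in ACiGaN, 10 months in CHRONiGaN.
- **Section 6.4:** 6 months in ACiGaN, 12 months in CHRONiGaN. The ACiGaN sample-size text in the synopsis and in section 6 also uses 6 months.

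**The concern.** A confirmatory trial that may stop early for benefit needs a stricter level at the interim than at a single final test. Otherwise the chance of a false claim exceeds the nominal 5%. This protocol permits such a stop and offers 0.05 as its only yardstick, so a reader applying it literally would test at 0.05 twice.

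The second problem is when the look happens. It is meant to be on the primary endpoint, yet it is triggered by 6 months of follow-up. In CHRONiGaN both arms receive RASBs alone for the first 4 months. A patient who has just reached month 6 has therefore had at most 2 months of differing treatment and has no primary outcome yet. A decision to stop CHRONiGaN for benefit or futility would rest on fewer outcomes than the 50% rule suggests.

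**Working it through.** **1. The plan's own figure.** Inputs from section 6: control mean change "in patients treated with RASBs alone (control arm) is 0.6", experimental "a mean delta proteinuria that is 1.2", SD 1.0 in both arms, and "132 patients (66 patients per group including a 10% dropout rate) for a power of 90%, a two-sided significance level of 0.05".

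- n per arm = 2 × ((1.960 + 1.282) × 1.0 / 0.6)² = 58.4, rounded up to 59.
- With 10% dropout: 59 / 0.90 = 65.6, rounded up to 66 per arm, or 132 in total.

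The figure is reproduced, and only by spending all of the two-sided 0.05 on one analysis.

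**2. Type I error with one interim at 0.05.** With information fraction t = 0.5, the interim and final statistics have correlation √0.5 = 0.707 under the null hypothesis.

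- Error = P(|Z₁| > 1.96) + P(|Z₁| ≤ 1.96 and |Z₂| > 1.96) = 0.0500 + 0.0331 = 0.0831.

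**3. If the 12-monthly analyses also tested efficacy at 0.05.** The accrual pattern is an assumption: uniform over the 36 months of recruitment. The share with the endpoint at calendar month T is (T − d)/36, where d is the endpoint time. The 50% trigger falls at 18 + 6 = month 24, which coincides with an annual look.

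| Endpoint time d | Information at the looks | Overall error |
|---|---|---|
| 4 months (ACiGaN) | 0.222, 0.556, 0.889, 1 | 12.4% |
| 6 months (ACiGaN) | 0.167, 0.500, 0.833, 1 | 13.1% |
| 8 months (ACiGaN) | 0.111, 0.444, 0.778, 1 | 13.7% |
| 10 months (CHRONiGaN) | 0.056, 0.389, 0.722, 1 | 14.4% |
| 12 months (CHRONiGaN) | 0.333, 0.667, 1 | 10.7% |

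If recruitment took 60 months (the two-year extension), the range would be about 14-18%.

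**4. What the trigger delivers in CHRONiGaN.** This assumes the same accrual, with the 50% counted within the trial. At month 24:

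- 10-month endpoint: (24 − 10)/36 = 38.9%, about 117 of 300, or 78% of the 150 patients who define the trigger.
- 12-month endpoint: (24 − 12)/36 = 33.3%, or 100 of 300.

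A month-6 value would not fill the gap. The visit grid in Figure 2B goes from month 4 to month 8, although section 4.4 says the endpoints are evaluated every three months in the first two years.

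**5. What the trigger delivers in ACiGaN.** At month 24 the share with data is 50% for the 6-month definition, 55.6% for 4 months and 44.4% for 8 months.

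**6. Limits that keep 5% with one look at half the information.** O'Brien-Fleming gives final z = 1.977 and interim z = 1.977/√0.5 = 2.797, which are two-sided p = 0.0480 and 0.0052.

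Power of the final test with 59 evaluable per arm is Φ(0.6/√(2/59) − z) = Φ(3.259 − z):

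- z = 1.960: 90.3%.
- z = 1.977: 90.0%.

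**The case against.** The best reply is that the 0.05 sentence is a general line in the methods section and is not tied to the interim. Numerical stopping limits are commonly left to an analysis plan or monitoring charter, neither of which is at hand, so their absence is not itself an error. That stands, and it makes the 8.3% conditional. It does not remove the point, because the protocol itself permits a stop for benefit and states one level with no exception.

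Four stronger readings are tempting but not supported:

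- **That every annual analysis is an efficacy test.** Only the 50% look is tied to the primary endpoint. Six equally spaced looks over six years would give 15.5%, but with 36-month accrual the primary-endpoint information is complete by month 40 to 48 (36 plus 4 to 12), so later annual looks would add nothing.
- **That the trigger fits neither trial.** Six months matches the ACiGaN definition in the synopsis sample-size text and in sections 6 and 6.4. The underlying fault is that the endpoint times conflict.
- **That no 10-month CHRONiGaN data would exist at the interim, or that the trial would be stopped on a 2-month contrast.** Earlier enrollees would have the endpoint, and section 7.3 nowhere substitutes a month-6 value for it.
- **That the Steering Committee will see results by arm.** Section 7.3 says only that data will be presented to it. It also says that the analysis is blinded, and section 7.4 says that monitoring members do not know the assignment. The sentence is ambiguous; it is not a stated disclosure.

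**Conclusion.** The point holds in limited form.

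- **Error rate:** as written, the protocol does not protect its 5% level. The error is 8.3% if 0.05 is used at one interim at half the information and again at the final. The 10.7-14.4% range needs two further conditions: efficacy tests at the 12-monthly analyses, and uniform accrual over 36 months.
- **CHRONiGaN timing:** the trigger does not secure the primary endpoint under either stated time. Under uniform accrual it yields 39% of the sample at 10 months or 33% at 12, instead of 50%.
- **ACiGaN timing:** whether the trigger fits depends on which of the protocol's own definitions is meant.

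The sample size of 132 is arithmetically correct for a single analysis at 0.05; the fault lies in the unadjusted repeat. It should be settled before the first comparative look, because an early claim of benefit under the present wording would be hard to defend.

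**What to change.** 1. Reconcile the primary time points first: 4 and 8 against 6 months in ACiGaN, and 10 against 12 in CHRONiGaN. The interim rule should follow whichever times the sponsor confirms.
2. Hold one efficacy look per trial, when 50% of that trial's patients have completed its confirmed primary time point.
3. Use O'Brien-Fleming limits: two-sided p<0.0052 at the interim and p<0.0480 at the final. If the information fraction turns out not to be 50%, use a Lan-DeMets spending function of O'Brien-Fleming type.
4. State that the 12-monthly reviews carry no efficacy test, and that futility is non-binding.
5. State that comparative interim results stay with the monitoring committee, and that the Steering Committee receives only a recommendation.

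The cost is protocol wording and about 0.3 percentage points of ACiGaN power (90.3% to 90.0% with 59 evaluable per arm, normal approximation), with no added patients. The CHRONiGaN interim moves later: under uniform accrual from month 24 to month 28 (18 + 10) or month 30 (18 + 12). CHRONiGaN states no power, so its power cost cannot be given.
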